The teams at Baycrest and JSLG will follow a similar protocol (for both users and informal caregivers) and will submit applications for ethics approval through the Baycrest Research Ethics Board and UCSF Institutional Review Board and the JSLG Research Committee.

Key Outcomes

Users

The key outcome measures of interest are the UCLA Loneliness Scale version 3,¹⁶ Duke's Social Support Index,¹⁷ and the Personal Health Questionnaire (PHQ-8).¹⁹ These outcomes will be measured at enrollment, week 9, and week 18.

Informal Caregivers

The primary outcome for informal caregivers will be their qualitative experiences, as discussed during a focus group or interview session. The evaluated impacts will be caregivers' experiences with the use of the ElliQ messaging function, the perceived changes (if any) on communication strategies between caregivers and their study partner (i.e., the ElliQ users), the perceived changes (if any) in the caregiver's ability to provide care for their study partner, and the perceived changes (if any) to the ElliQ user's social engagement, loneliness, well-being, and access to and use of technology.

Sample Size

Users

According to Russell¹⁶ the mean and standard deviation of the UCLA Loneliness version 3 score for a general older adult population is 31.51 and 6.92, respectively. Assumptions for the sample size calculation include a 2x2 factorial design to anticipate potential site differences, a 5.0-point mean difference in the mean change in the UCLA Loneliness Scale version 3 score between the ElliQ intervention and waitlist control groups, and a standard deviation of 15.0 to account for a 2x higher variability compared to Russell's (1996) reported value. For a mean difference of 5.0 and a standard deviation of 15.0, a medium effect size of 0.33 was used to obtain the required sample size.

Using the PASS 16 sample size calculator, a total sample size of 76 (38 per intervention group, 19 per cell in a 2x2 factorial design) achieves 81% power when F tests are used to test the intervention factor (ElliQ versus Waitlist control), site factor (Baycrest versus JSLG), and intervention–site interaction at a 5% significance level and an effect size of 0.33. It is recommended that the ElliQ study recruit a total of 96 participants (48 per intervention group, 24 per cell in a 2x2 factorial design, Table 1) with a contingency of up to a 20% dropout rate (20 expected dropouts).

Table 1. Number of participants to recruit

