Baseline characteristics of the participants in the two intervention groups will be summarized by site through descriptive statistics, frequencies, or proportions. Comparisons between intervention groups and between sites will be performed to determine whether a balance between intervention groups has been achieved as a result of the randomization process conducted at the site level. Analyses will include independent *t*-tests for continuous data or chi-squared tests for proportions. If the distribution of any continuous measure is markedly skewed or contingency tables for proportions contain cell sizes <5, non-parametric tests, namely the Mann–Whitney U/Wilcoxon rank-sum test and Fisher's exact test, will be conducted in place of the independent *t*-test and chi-squared test, respectively.

Primary Analysis (Users)

Analysis of the effect of the intervention on the key outcome measures will be performed using an intent-to-treat approach, thus including all randomized participants. The primary analysis will include participants in the ElliQ intervention group and the comparable contemporary waitlist control. If there is balance in participants' characteristics across the two sites, evaluation of changes in the outcomes will only include the intervention as the independent variable of interest. In this case, the mean change in the outcome scores from Baseline to Post 1 (Session 2) will be calculated for each intervention group. The calculated mean change will be compared between intervention groups using an independent *t*-test. Effect sizes within an intervention group (standardized response means) and between groups will be calculated to measure the magnitude of mean differences. In the case of an imbalance between sites, the primary analysis will be a linear regression model involving the change in primary outcome as a function of intervention, site, and intervention–site interaction. Measurements of the primary outcome obtained at Time 3 for the ElliQ intervention group and on the waitlist control after being given ElliQ will not be included in this primary analysis.

Sub-Analyses (Users and Informal Caregivers)

Sub-analyses will involve the assessment of the outcomes when participants are exposed to ElliQ and evaluating differences in the trends in bi-weekly engagement survey responses between intervention groups.

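### The 81% power figure comes from entering a standardised mean difference (5/15 = 0.33) as the F-test effect size; at the plan's own inputs 76 completers give about 30% power

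*Combined protocol and SAP*

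**What the plan says.** The Sample Size section (Users) of the combined protocol and SAP sets the planning effect as "a 5.0-point mean difference in the mean change in the UCLA Loneliness Scale version 3 score between the ElliQ intervention and waitlist control groups". It takes an SD of 15.0, described as roughly doubling the published SD of 6.92 for a general older population. It combines the two: "For a mean difference of 5.0 and a standard deviation of 15.0, a medium effect size of 0.33 was used". From that it concludes that "a total sample size of 76 (38 per intervention group, 19 per cell in a 2x2 factorial design) achieves 81% power", with F tests for intervention, site and their interaction at the 5% level. Recruitment is then raised to 96 to allow for 20% dropout, and Table 1 sets out the resulting cells. The Recruitment section aims for 100.

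Under Data Analysis, Primary Analysis (Users), the outcome is the change from baseline to the second session. If the sites are balanced, the plan is: "The calculated mean change will be compared between intervention groups using an independent" t-test. If they are not, it is a linear regression on intervention, site and their interaction. Time 3 data are excluded from this comparison.

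**The concern.** Two effect-size scales appear to have been confused. A difference divided by an SD is d. An F-test power routine expects f, the SD of the group means divided by the within-group SD. For two equal groups the means lie half the difference either side of the grand mean, so f = d/2. If 0.33 was entered as f, the calculation powered the trial for a difference twice the one stated.

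This paragraph is the only justification given for the number of users randomised. It also presents the design as cautious, because the SD was deliberately raised to about twice the published value. Doubling the effect size has the same effect on power as halving the SD, so the substitution cancels that caution. A reader who trusts the 81% could take a non-significant result as fair evidence against a 5-point benefit when, at the stated SD, the design would usually miss one.

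**Working it through.** **Inputs, all from Sample Size (Users):** difference in mean change 5.0; SD 15.0; effect size 0.33; N = 76 (38 per group, 19 per cell); 5% significance level; stated power 81%.

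**Method.** The intervention effect in a 2x2 layout has 1 numerator df and N − 4 = 72 error df. Power is the probability that a noncentral F with noncentrality λ = N × f² exceeds the 5% critical value of the central F, which is 3.97.

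**Step 1: reproduce the plan's figure.** With f = 0.33, λ = 76 × 0.33² = 8.28 and power is 81.0%, which matches. With N = 72 the same calculation gives 78.8%, so 76 is the smallest N with equal cells that passes 80%. Both the 76 and the 81% therefore follow from using 0.33 as f.

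**Step 2: convert the stated inputs to f.** d = 5.0/15.0 = 0.333, so f = 0.333/2 = 0.167.

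**Step 3: recompute at the stated inputs.**

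| Analysed N | λ = N × 0.167² | Power |
|---|---|---|
| 76 | 2.11 | 30.0% |
| 96 (no dropout) | 2.67 | 36.6% |
| 100 (no dropout) | 2.78 | 37.8% |

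The two-sample t-test of the primary analysis (74 df) also gives 30.0% at N = 76.

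**Step 4: what 76 completers can detect with 81% power.** This needs f = 0.33, so d = 2 × 0.33 = 0.66. At SD 15 the difference is 0.66 × 15 = 9.9 points. For a 5-point difference the SD of change must be 5/0.66 = 7.6.

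**Step 5: size needed for 5 points at SD 15.** The normal approximation gives 142 per group, or 284 completers, for 80% power. The 2x2 F test gives 79.9% at 284 and 80.5% at 288.

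**Step 6: look for another reading that gives 81%.**
- A one-sided t-test at the stated inputs gives about 42%, and the plan does not specify one.
- A 3-df F test across the four cells at f = 0.33 gives 64%.
- Suppose 15 is the SD of a single score, which the section does not say. The SD of change is then 15 × √(2(1 − r)), where r is the correlation between visits. Power is 30% at r = 0.5, 46% at r = 0.7 and 62% at r = 0.8, and reaches 80% only near r = 0.87. The documents give no value for r.

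None of these gives 81% from the stated inputs.

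**The case against.** The arithmetic is hard to dispute, so the best defence concerns what follows from it. SD 15 is a deliberately inflated assumption, and the true SD of change may be much smaller. For 5 points with 76 completers, power is 87% at SD 6.92, 77% at SD 8, 58% at SD 10 and 43% at SD 12. The trial is therefore not shown to be underpowered in practice. The 81% is also a correct power for f = 0.33; the faulty step is equating 5/15 with f. Finally, the plan reports effect sizes alongside the test, and nothing in it says a null result will be read as evidence of no benefit.

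All of this stands as a limit on the claim. The low power holds if the SD of change is 15, and the risk of misreading is an inference. It does not rescue the paragraph, which states the SD and the difference and attaches to them a power they do not yield. A smaller SD could be a reasonable planning value, but the plan would have to state and justify it, and the present text assumes the opposite. Asking for a new SD also carries a risk: about 7.6 is the value that restores 81%, so a figure near it needs a source independent of this calculation.

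**Conclusion.** The concern holds. The sample-size calculation used d where f was required. For a 5-point difference with an SD of change of 15, at a two-sided 5% level, 76 completers give 30.0% power, not 81%. The design would miss such a benefit about 7 times in 10. Full retention of 96 or 100 participants raises power only to 36.6% or 37.8%.

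The result rests on the plan's own difference, SD, sample size and significance level, on equal groups, and on reading 15 as the SD of the change score, which is how the section pairs it with the difference. It shows that the stated justification is wrong under its own inputs. Actual power depends on an SD of change that the documents do not supply.

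**What to change.** Rewrite the sample-size paragraph and leave N as it is. State that the effect size is d = 0.33, equivalent to f = 0.167, and replace the power statement. Suggested wording:

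*With 76 completers and a two-sided 5% level, power for a 5-point difference in mean change is 30% if the SD of change is 15, 58% if it is 10, and 81% if it is about 7.6. If the SD of change is 15, 81% power is reached for a difference of about 9.9 points.*

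If 5 points remains the target and a smaller SD is to be the planning value, give a source for the SD of change, or for the correlation between visits, that does not depend on the power it produces. Keep the range of SDs in the text either way.

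The cost is one reworded paragraph. No participants are added and neither the design nor the primary analysis changes. The stated power, or the detectable difference, becomes less favourable. Keeping both 5 points and SD 15 at 80% power would instead need about 284 to 288 completers, or 355 to 360 recruited at 20% dropout (284/0.8 and 288/0.8).

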Those who get assigned to the second (waitlist) condition will attend an initial baseline data-collection session (time 1; week 0), where questionnaires related to participant characteristics and baseline measures will be administered. Participants will then wait for 8 weeks to get the ElliQ device (weeks 1–8). After this 8-week wait, participants will be invited to attend another data-collection session (time 2; week 9), where they will be asked to complete some of the same measures that they completed at time 1. Following this session, participants will trial the device for 8 weeks (weeks 10–17). After the 8-week trial, participants will be asked to attend a post-trial data-collection session (time 3; week 18), where they will return the ElliQ system. Participants will then complete a number of the same measures that were completed at times 1 and 2, and attend a one-time, audio-recorded focus group or interview session, where field notes will be taken.

Upon completion of the study tasks (i.e., at the final data-collection session at week 18), each participant's study participation will conclude.

Informal Caregivers

Informal caregivers (e.g., family, friends who provide care for the ElliQ user) may also be enrolled in the study to investigate their experiences with the messaging function of the ElliQ system (user and caregiver pairs will be referred to as “dyads” going forward). Of note, users who do not have caregivers can still enroll in the study.

This will be an exploratory study, insofar as eligible and consented informal caregivers will complete a baseline data collection session for participant characterization; they will also have the opportunity to test the ElliQ messaging function for the 2 months while their study partner (i.e., the ElliQ user) tests the ElliQ system. Informal caregivers will have the opportunity to discuss their ElliQ experience, caregiving experience, and their perception of the impacts the ElliQ system and messaging function had on their study partner's social engagement, loneliness, access to technology, and use of different communication methods (e.g., online, in-person, over the phone, etc.). An audio-recorded focus group or interview (where field notes will be taken) will be held with informal caregivers at the end of the ElliQ users' 2-month test/use period (i.e., on or around week 9 for caregivers of users in the intervention group, or on or around week 18 for caregivers of users in the waitlist control group).

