Study participants (users) will be asked by the research staff if they have an informal caregiver (e.g., a family member or friend who provides care for them) who might be interested in taking part in the study as well. Those participants who indicate that they do have an informal caregiver who might be interested will be provided with the research staff's contact information to share with their informal caregiver. Interested caregivers who contact the research staff will be provided with more information about the study either over the phone, in person, or over email. Users who do not have informal caregivers can still take part in the study and will not have access to the messaging function.

Study Population: Eligibility Criteria

Inclusion Criteria (Users):

- Older adults aged ≥ 70 years old and living alone
- Has minimal exposure to technology on a daily basis
- Residents of Baycrest or JSLG/UCSF, or community-dwelling older adults who live near Baycrest or JSLG/UCSF
- Agrees to allow the ElliQ setup team (a member of Baycrest or JSLG/UCSF and Intuition Robotics) to come to their home to install the ElliQ system and to provide training on how to use the system
- Agrees to have the ElliQ setup team test their existing Wi-Fi in their home or agrees to allow for installation of Wi-Fi in their home for the duration of the study (at no cost to the participant)
- Is able to speak clearly and be understood, as exemplified by an app such as Siri/Google speech recognition
- Is able to hear a finger rub with hearing aids in, if applicable
- Is able to read visual content on a screen

Exclusion Criteria (Users):

- Is unable to communicate in oral English
- Is unable to read visual content on a screen
- Has a history or current diagnosis of major psychiatric conditions, excluding depression
- Has sensory impairments (e.g., severe auditory or visual impairments) that would impede an individual's ability to interact with the ElliQ system, which features voice-activated technology and the presentation of content on a screen
- Has an MMSE score < 18
- Is currently enrolled in another study

Inclusion Criteria (Informal Caregivers):

- Is an informal caregiver (e.g., a family member, friend, etc.) of an ElliQ study participant
- Lives separately (in a different home) from their study partner (i.e., the ElliQ participant)
- Has access to an Android Smartphone or iPhone running iOS v. 10 or above through which to access Twilio Messenger.

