- Is willing and able to use Twilio Messenger to access the ElliQ messaging function
- Understands and abides by the terms and conditions of the messaging app (i.e., Twilio messenger) that links to the ElliQ system
- Is able to speak clearly and in oral English
- Able to hear audio and see and read content on a screen

Exclusion Criteria (Informal Caregivers):

- Individuals who are not an informal caregiver to an ElliQ study participant
- Lives in the same home as the ElliQ study participant
- Does not have access to an Android Smartphone or iPhone running iOS v. 10 or above through which to access Twilio Messenger
- Is unable or unwilling to use Twilio Messenger to access the ElliQ messaging function
- Refuses to abide by the terms and conditions of Twilio Messenger
- Is unable to speak or read in English
- Is unable to hear audio or see/read content on a screen

Randomization

Users

Once participants have been screened, deemed eligible for the study, completed the informed consent process, and have completed the preliminary baseline measures, they will be randomly assigned to either the active condition or a waitlist control group. Stratified randomization with allocation concealment will be implemented in the study. Separate randomization schedules containing unique three-digit numbers with corresponding 1:1 intervention allocation will be generated by a biostatistician at Baycrest using SAS 9.4. Each site (Baycrest and JSLG) will receive randomization schedules for up to 50 participants. The point persons at Baycrest and JSLG will obtain the randomization schedule for their respective sites. The point person(s) at each site will prepare 50 opaque sealed envelopes each containing a unique three-digit number from their site-specific randomization schedule and will give these envelopes to the recruiting research assistants. Once an eligible individual consents to participate in the study, the recruiting research assistant will pick a sealed envelope and use the three-digit number as the consenting participant's study ID. The recruiting research assistant must coordinate promptly with the point person in charge of keeping the randomization schedule to determine the intervention allocation assigned to the specific three-digit number obtained. The research assistant will then inform the consenting and eligible participant regarding their intervention group assignment and proceed with the next steps of study implementation.

ElliQ Implementation

Users

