Those informal caregivers who enroll in the study will attend a baseline session of up to 1 hour immediately after the informed consent process. At this session, informal caregivers will be trained on how to access and use Twilio Messenger as part of the ElliQ messaging function. They will be instructed to use the function for as long as they feel comfortable and willing to do so for the duration of their study partner's 2-month ElliQ test/use period. Informal caregivers will be provided with study staff's contact information, should they have any questions about the device or the study. They will also be informed that they can take as much time as they need to review Twilio's terms of service and privacy statement before agreeing to use the messaging function (where messaging data will be captured and stored by Twilio and not collected, accessed, or used for study purposes).

Data Collection

Users

The following data will be collected as part of the study.

Time 1 (Baseline and Participant Characterization)

Medical/Study Data

- Participant characterization
 - a) Demographics questionnaire
 - b) SF-12¹²
 - c) Lawton's IADL Scale¹³
 - d) Mini-Mental State Examination (MMSE)¹⁴
 - e) Caregiver status questions
- Access to technology/technology literacy
 - a) Computer Proficiency Questionnaire¹⁵
- Loneliness and social isolation
 - a) UCLA Loneliness V3 Scale¹⁶
 - b) Duke's Social Support Scale¹⁷
- Quality of life
 - a) OPQOL¹⁸
- Mood
 - a) Personal Health Questionnaire (PHQ)-8¹⁹
 - b) Visual Analog Mood Scale (VAMS)²⁰
 - c) Brief Mood Introspection Scale (BMIS)²¹

During the Study Period

Product Usage Data (Captured by ElliQ)

The ElliQ system is capable of capturing data on its own, as per its commercially available functions. There are two primary types of data that the ElliQ system can capture; for example:

Product Usage Data – Metrics

- Number of proactive plans initiated by the ElliQ system (e.g., when the ElliQ system initiates small talk or suggests an activity)
- Number of reactive plans (i.e., ElliQ responding to the user)

- Plan context (proactive or reactive)
- Plan type (video, small talk, other)
- Total number of plans per time unit
- Time and date of plan
- The time the device is turned on or off

Product Usage Data – Personal Interactions

- Facial recognition
- IP address
- Speech intent (mapped to ElliQ’s library of intent types)
- TextHeard (speech-to-text data)

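### The envelope step is triggered by consent, while the same section requires baseline measures before assignment; the trigger should be completion of all Time 1 measures

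*Combined protocol and SAP*

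**What the plan says.** Under Randomization (Users), the opening sentence lists what must come before assignment: screening, eligibility, consent and baseline. People who meet the first three and "have completed the preliminary baseline measures, they will be randomly assigned to either the active condition or a waitlist control group".

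The mechanics later in that paragraph start from a different event: "Once an eligible individual consents to participate in the study, the recruiting research assistant will pick a sealed envelope and use the three-digit number". That number becomes the participant's study ID. The assistant then "must coordinate promptly with the point person in charge of keeping the randomization schedule to determine the intervention allocation" for that number. Next comes disclosure: "The research assistant will then inform the consenting and eligible participant regarding their intervention group assignment and proceed with the next steps". Baseline completion is not mentioned in these steps.

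Under Study Design (Users), the waitlist arm is introduced thus: "Those who get assigned to the second (waitlist) condition will attend an initial baseline data-collection session" at week 0. The ElliQ arm is likewise described as a group whose members first have their baseline session and shortly afterwards receive the device.

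Key Outcomes (Users) places the first measurement of the UCLA Loneliness Scale, the Duke index and the PHQ-8 at enrollment. Primary Analysis (Users) compares mean change from baseline to Session 2 with an independent t-test. If the sites are imbalanced, it regresses that change on intervention, site and their interaction.

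**The concern.** The order of baseline and disclosure cannot be reversed once it has happened. The instructions that a research assistant would carry out run from consent to envelope, to look-up, to telling the participant. Someone working from those steps alone would not learn that baseline must be finished first.

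Three features of the design make this matter. Participants are told their group. The key outcomes are questionnaire scales that they answer themselves. The baseline score is half of the endpoint, because the primary analysis uses change and neither version of it includes a baseline covariate. A person who has just heard that the device is coming now, or in eight weeks, may answer questions on loneliness or mood differently. If that reaction differs between arms at baseline and has faded by Time 2, the difference in change scores contains it. A score already affected by knowledge of the group cannot be put right in the analysis.

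**Working it through.** **Step 1. The order of events, place by place.**

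| Place | Event that leads to assignment | Is baseline placed before disclosure? |
|---|---|---|
| Randomization (Users), opening sentence | Screening, eligibility, consent, baseline measures | Yes, explicitly |
| Randomization (Users), envelope step | Consent of an eligible person | Not stated |
| Randomization (Users), look-up and disclosure | The envelope draw, then prompt contact with the list holder | Not stated; no baseline step in between |
| Study Design (Users), both arms | None; people are described by group, then attend baseline | Not settled; fits either order |
| Key Outcomes (Users) | None; first measurement at enrollment | Not settled |

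Only the first row sets an order. The second and third rows can be followed to the letter without it.

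**Step 2. How a baseline reaction enters the estimate.** Let δ be the between-arm difference in baseline score caused by knowing the group, and let p be the fraction of it still present at Time 2. The between-arm difference in change is then displaced, in absolute size, by

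bias = δ × (1 − p).

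If p = 1 the reaction cancels. If p = 0 it passes through in full. With p = 0, each point of δ moves the estimate by 1 point, which is 1/5.0 = 20% of the planned 5.0-point difference.

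**Step 3. Illustration of size.** This point does not turn on any figure in the plan. The planning inputs are taken from Sample Size (Users): 38 per group, SD 15.0, 5% significance. As background, the stated 81% power is reproduced by a noncentral F with 1 and 72 degrees of freedom and noncentrality 76 × 0.33² = 8.28, which gives 0.810.

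For a two-sample t-test with no true effect:

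- SE = SD × √(2/38). At SD 15.0 this is 15.0 × 0.2294 = 3.44.
- Degrees of freedom = 2 × 38 − 2 = 74.
- Noncentrality = bias/SE. For a bias of 2 points, 2/3.44 = 0.58.
- The type I error is the two-sided rejection probability under the noncentral t.

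The documents give neither δ nor p, so the biases below are assumptions. The second SD, 6.92, is the one that the plan cites for scores in a general older population. It is used here only as an assumed low value for the SD of change, where SE = 6.92 × 0.2294 = 1.59.

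| Assumed bias δ(1 − p) | Type I error, SD 15.0 | Type I error, SD 6.92 |
|---|---|---|
| 0 | 5.0% | 5.0% |
| 1 point | 5.9% | 9.5% |
| 2 points | 8.8% | 23.8% |
| 3 points | 13.8% | 46.2% |

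A 2-point shift that has wholly gone by Time 2 corresponds to the 2-point row. If half of it persists, the bias is 2 × 0.5 = 1 point and the 1-point row applies.

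**The case against.** The strongest reply is that the section opens with an explicit rule, and that the envelope sentence only describes mechanics and takes the rule for granted. It omits baseline, but it does not say that baseline follows. No sentence states that the group is disclosed at the consent visit, and the call for promptness governs contact with the list holder after the draw, not the interval since consent. All of this stands. The intended design is baseline first, and collecting baseline after disclosure is a risk of literal reading, not a stated plan. What remains is that the operating steps name a different trigger from the rule, and that staff carry out the operating steps.

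Three stronger readings are tempting, but the documents do not support them.

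- *That the Study Design text proves assignment before baseline.* Describing each arm's schedule by its eventual group is ordinary protocol style. That text fits either order and so neither causes the conflict nor resolves it.
- *That people would be excluded on the MMSE after randomization, which would break the inclusion of all randomized participants.* The MMSE is listed as a Time 1 measure, and the exclusion criterion is "Has an MMSE score < 18". But the draw applies only to an eligible individual, so the criterion must already have been checked. If anything, this implies that part of Time 1 comes before the draw.
- *That the envelope must be drawn early because its number is needed on the baseline forms.* The number becomes the study ID, but nothing says how baseline forms are labelled.

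It is also fair to say that the error rates above are not properties of the plan. They depend on an assumed shift and on how much of it fades.

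**Conclusion.** The inconsistency is real and lies within one section: baseline completion is required by the opening sentence and absent from the steps that put it into effect. The consequence is conditional. It needs staff to follow the operating steps literally, participants in the two arms to react differently to learning their group, and that reaction to fade at least in part by Time 2. Its direction cannot be inferred from the documents. Under the assumed 2-point shift with complete fading, the type I error is about 9% rather than 5% at the plan's SD and 38 per arm. Less fading gives less inflation, and a smaller SD of change gives more. The point calls for a correction before enrollment because the primary endpoint is exposed and the remedy is nearly free. It does not show that the trial intends to collect baseline after disclosure.

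**What to change.** In Randomization (Users), replace the trigger of the envelope step. Suggested text: *After an eligible person has given consent and every Time 1 measure is complete, the research assistant draws a sealed envelope.* State that contact with the list holder and disclosure of the group take place only after that draw.

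In Study Design (Users), reword the two arm descriptions so that the Time 1 session is described once, for everyone, before assignment.

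An optional safeguard is a screening ID issued before the draw, so that the randomization number has no use until baseline is finished.

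The cost is a few sentences of protocol wording and, if the option is taken, one extra identifier. No visits, measures or staff are added, and the sample size does not change.
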